4.4 Conclusions

The BIO|CONCEPT AlCath Force post-market clinical study demonstrated the AlCath Force Sensing Ablation Catheter and the Qubic Force Sensing Module were safe and effective. Although a small sample size was studied, no serious adverse device effects were noted. Acute outcomes were 100% and 94.4% for the AF and AFL populations, respectively. The clinical study did not evaluate long-term arrhythmia management effectiveness.

5 STUDY DEVICE DESCRIPTION

5.1 Indication for Use (proposed)

The AcQBlate[®] FORCE Sensing Ablation Catheter and related accessory devices are indicated for cardiac electrophysiological mapping, delivery of diagnostic pacing stimuli, and radiofrequency ablation of recurrent and symptomatic atrial flutter (AFL) when used with a compatible RF Generator. When used with the Qubic Force[®] module, the AcQBlate[®] FORCE Sensing Ablation Catheter provides a real time measurement of contact force between the catheter tip and the heart.

5.2 AcQBlate[®] Force Sensing Ablation System

The AcQBlate[®] Force Sensing Ablation System (herein known as AcQBlate Force Sensing System) comprises the AcQBlate Force Sensing Ablation Catheter (AcQBlate[®] FORCE), the Qubic Force Sensing Module (Qubic Force), the Qubic RF Generator, and the Qiona Irrigation Pump with Tubing Set. The System is designed for EP mapping and RF ablation of typical atrial flutter.

5.3 AcQBlate Force Sensing Ablation Catheter

The AcQBlate Force is a unidirectionally deflectable, steerable, quadripolar, irrigated ablation catheter with an integrated force sensor for intracardiac application. It is designed for EP mapping and RF ablation of cardiac arrhythmias.

5.3.1 Qubic Force Sensing Module

The AcQBlate FORCE contact force monitoring capability requires connection with the Qubic Force Sensing Module (Qubic Force) by means of an optical cable which is permanently attached to the catheter.

The Qubic Force is a non-sterile, reusable unit that does not contact the patient . It processes the contact force signal from the AcQBlate FORCE during an EP procedure irrespective of an RF energy application (ablation).

5.4 Qubic Radiofrequency (RF) Generator

The Qubic RF Generator is a modular RF generator that can be used in combination with the AcQBlate FORCE for cardiac RF ablation. The values measured during ablation are shown on the display and control unit screen.

5.5 Qiona Irrigation Pump and Tubing Set

The Qiona Ablation Irrigation Pump is used in conjunction with a tubing set to deliver a sterile 0.9% sodium chloride solution (normal saline) for the purpose of cooling the AlCath Flux catheter tip during ablation procedures.

5.6 The AcQBlate Force System Operation

General

Equipment used during an EP procedure may include devices for introduction of the catheter into the vascular system, catheter visualization, processing the EP signals, and devices providing electrical stimulation for diagnostic purposes. In this clinical study, the AcQBlate FORCE catheter will be used with the Qubic Force, the Qubic RF Generator and the Qiona Ablation Irrigation Pump with Tubing Set . These devices are not FDA approved and therefore considered investigational devices.

In a typical ablation procedure, EP mapping is performed to identify and map the arrhythmogenic areas in the heart to be targeted for subsequent ablation. All catheter manipulations during mapping and ablation should be performed with a navigational guidance (fluoroscopic, intracardiac echo and/or 3D navigation devices).

Electrophysiologic Mapping

Prior to the actual ablation, diagnostic EP mapping may be performed with the AcQBlate FORCE. During this process, the contact force information provided by the Qubic Force may be used to monitor the contact between the catheter tip and the myocardial tissue and may assist the operator to obtain stable intracardiac signals of appropriate quality. Moreover,

contact force monitoring may reduce the risk of cardiac perforation as a result of excessive contact force. During EP mapping the electrodes of the AcQBlate FORCE can be used for pacing. Procedures and routines used during the mapping procedure strongly depend on the arrhythmia(s) to be treated.

Advanced Mapping Systems

The AcQBlate Force System is compatible with the Acutus Medical AcQMap System with investigational frame software v3.6.4.XX. Use of the AcQMap System with the investigational frame software may be utilized to support display of ablation parameters. The ablation specific data includes the below listed parameters:

- Contact force from Qubic Force •
- Power from Qubic RF
- AcQTag – used to color and size markers automatically on the 3D anatomy model
- Listing of generic auxiliary catheters •

The AcQMap System with the investigational frame software is considered part of the investigational device and is an optional accessory to the AcQBlate Force System. Use of the AcQMap System with investigational frame software v3.6.4.XX should be at the discretion of the Investigator.

RF Ablation

Once the targets for ablation have been appropriately identified, ablation is performed using the AcQBlate FORCE ablation functionality. The ablation electrode at the tip of the catheter is positioned by means of the steering mechanism on the proximal handle and RF current is applied by the Qubic RF generator. RF application is a functionality of the Qubic RF generator, not directly controlled by the AcQBlate FORCE catheter. Irrigated ablation catheters like the AcQBlate FORCE are used in power-controlled mode. In this mode, the supply of RF current is regulated and/or discontinued if the power exceeds a user-defined threshold. Additionally, a temperature cut-off is set to define a maximum catheter tip temperature to stop RF delivery in case of overheat. This may reduce the risk of steam pops and cardiac perforation as well as prevent excessive scar formation and thermal coagulation of blood at the ablation site.

The contact force shown by the Qubic Force is an indication of the quality of the contact between the ablation electrode and the myocardial tissue. The operator may use the contact force information to monitor the tissue-electrode contact and achieve effective lesion creation while minimizing the risk of cardiac perforation. The direction of the total contact force vector indicated by the Qubic Force may assist the operator to control the orientation of the AcQBlate FORCE regarding the tissue. For instance, a perpendicular orientation of the CONFIDENTIAL

ablation electrode would be indicated by a minimal lateral force component. In addition, the FTI parameter informs the operator about the stability of the catheter tip on the tissue, which contributes to the effectiveness of lesion creation.

The tip design of the AcQBlate FORCE allows the application of a heparinized saline flow to be dispensed through the irrigation holes of the tip. Irrigated RF ablation is intended to allow the application of a relatively high RF power without overheating the tissue surface. This may increase the effectiveness of lesion creation.

As part of the manufacturing process, each AcQBlate FORCE is individually calibrated in order to associate the optical signal with the actual contact force. This calibration data and additional manufacturing data are stored in an RFID chip integrated in the fiber optics connector of the AcQBlate FORCE. Upon connection of the AcQBlate FORCE with the Qubic Force, these data are automatically read by the Qubic Force and used to provide catheter-specific, calibrated contact force information. As a result, a separate calibration procedure before using the catheter is not required, and the contact force reading is accurate after zero-setting the contact force while the AcQBlate FORCE is free-floating in the heart chamber (i.e., no contact with the cardiac wall).

5.7 Investigational Devices

Table 5describes the investigation devices and cables that will be used as part of the AcQForce Flutter study.

Product(s)	Model(s)
AcQBlate FORCE (Acutus)	900202, 900203, 900204, 900205, 900206
Qubic Force (Acutus)	900012
Qiona Irrigation Pump (Biotronik)	406935
Qiona Irrigation Tubing Set (Biotronik)	365775
Qubic RF Generator (Biotronik)	396166
Qubic RF Foot Switch (Biotronik)	404964
Power cord US	NK-11*
Cable for recording system analog connection (analog signal cable that transmits the ECG signals of the ablation catheter to the Recording System, where all ECG signals are collected and displayed)	MPK-4-R *
Neutral electrode/grounding pad	PK-153*
Patient cable to connect Qubic Force or Qubic RF to AcQBlate FORCE	PK-147*
Cable to grounding or neutral electrode (connects the neutral electrode, a patch usually on the leg of the patient, with the generator to close the current loop between catheter-patient-generator)	PK-148*
Cable to control unit to the Qubic RF unit (ethernet cable to connect the RF generator and the remote unit's digital communication)	VK-118*
Cable for connecting the Qiona Irrigation pump to the RF unit	VK-119*
Cable for connecting the Qubic RF unit to an EP recording system digital connection	VK-120*
Video Cable for Connecting an External Monitor to Qubic Force	VK-124*
Adapter Cable for connecting AcQMap to Qubic RF	800630*

Table 5. Investigational Devices and Cables with Product Numbers

*Or sponsor specific equivalent

6 CLINICAL INVESTIGATIONAL PLAN/ PROTOCOL

6.1 Clinical Study Objective

The objective of the study is to demonstrate the AcQBlate Force Sensing System is safe and effective when used to ablate the cavotricuspid isthmus (CTI) for the treatment of typical atrial flutter when compared to a literature-based control.

Data will be used to support a PMA application.

6.2 Clinical Study Design

The AcQForce Flutter clinical study is a prospective, multi-center, non-randomized global clinical study designed to demonstrate the safety and efficacy of the AcQBlate Force Sensing Ablation System in the ablation management of symptomatic cavotricuspid isthmus dependent atrial flutter. The subject population will consist of men and women 18 years of age or older, presenting for a *de novo* percutaneous cardiac ablation of symptomatic, typical atrial flutter.

6.3 Primary Endpoints

6.3.1 Safety

The Primary Safety Endpoint for the AcQForce Flutter study is a comparative analysis of subjects who are free from a composite list of pre-specified device/procedure related Serious Adverse Events (SAEs) that occur through 7-days post ablation procedure using a literature-based control.

Serious adverse events are pre-defined and include:

- Death
- Cardiac tamponade/perforation
- Myocardial infarction
- Stroke
- Systemic embolism
- Major access site complications
- Major bleeding requiring transfusion
- Complete heart block
- Other SAEs/SADEs adjudicated by an independent review as "probably or definitely related" to the Investigational device.

All adverse clinical events will be collected, coded and reported, for the duration of the study according to the definitions of EN ISO 14155. The occurrence rate for all the clinical events will be characterized and calculated by independent adjudication. Table 6 outlines SAE definitions.

SAE	Study Definition		
Death	Cessation of life		
Cardiac tamponade/perforation	 Development of a significant pericardial effusion during or within 30-days of the procedure. A significant pericardial effusion is one that results in: hemodynamic compromise; or requires elective or urgent pericardiocentesis; or results in a 1 cm or more pericardial effusion as documented by echocardiography. 		
Myocardial Infarction	 Presence of any one of the following criteria: detection of ECG changes indicative of new ischemia (new ST T wave changes or new left bundle branch block (LBBB)) that persist for more than 1 hour; development of new pathological Q waves on an ECG; imaging evidence of new loss of viable myocardium or new regional wall motion abnormality. 		
Stroke	 Rapid onset of a focal or global neurological deficit with at least one of the following: change in level of consciousness. hemiplegia, hemiparesis, numbness or sensory loss affecting one side of the body; dysphasia or aphasia, hemianopia, amaurosis fugax; other neurological signs or symptoms consistent with stroke. 		
	Duration of a focal or global neurological deficit should be > 24 hours (less if therapeutic intervention(s) were performed (e.g., thrombolytic therapy or intracranial angioplasty)).		
	Confirmation of the diagnosis by at least one of the following:		
	 neurology or neurosurgical specialist; neuroimaging procedure (Magnetic resonance imaging (MRI) or computed tomography (CT) scan or cerebral angiography; lumbar puncture (i.e., spinal fluid analysis diagnostic of intracranial hemorrhage). 		

Table 6. Serious Adverse Event Definitions

Systemic embolism	Acute vascular insufficiency or occlusion of the extremities or any non-CNS organ associated with clinical, imaging, surgical/autopsy evidence of arterial occlusion in the absence of other likely mechanism (e.g. trauma, atherosclerosis, or instrumentation). When there is presence of prior peripheral artery disease, angiographic, surgical or autopsy evidence is required to show abrupt arterial occlusion.
Major access site complications	Vascular access complications include development of a hematoma, an arteriovenous (AV) fistula, or a pseudoaneurysm. A major vascular complication is defined as one that requires surgical or pharmacologic intervention.
Major bleeding requiring transfusion	Significant bleeding that requires and/or is treated with transfusion of blood products (≥ 2 units).
Complete heart block	Cardiac conduction block of the AV node requiring the implantation of a permanent pacemaker.
Other SAEs/SADEs	A complication that results in permanent injury or death,
adjudicated by an	requires intervention for treatment, or prolongs or requires
independent review as	hospitalization for more than 48-hours.
"probably or definitely	
related" to the	
Investigational device.	

6.3.2 Efficacy

The Primary Effectiveness Endpoint for the AcQForce Flutter study is an analysis of subjects achieving acute procedural success. Acute procedural success is defined as the demonstration of bidirectional cavotricuspid isthmus block at least twenty (20) minutes following the last radiofrequency application at the cavotricuspid isthmus with the investigational catheter.

Bidirectional block (BDB) confirmation is defined as:

• Demonstration of bidirectional electrophysiological conduction block through the cavotricuspid isthmus (CTI) using both coronary sinus ostium (CS) and annular low right atrial pacing maneuvers.

6.3.2.1 Primary Efficacy Endpoint Failure

A primary efficacy failure will comprise the following:

• The inability to achieve and maintain bidirectional CTI block at least 20 minutes following the last RF application with the investigation device. A second investigative catheter or alternate catheter curve may be used prior to designation as failure. Maximum RF time before considering a non-investigational catheter is at the discretion of the Investigator but shall not exceed 60 minutes of RF time.

OR

• The use of a commercially available non-investigational catheter for any ablation of the CTI.

NOTE: Use of isoproterenol is at the discretion of the Investigator.

6.3.2.2 Observational Effectiveness Endpoint

The observational effectiveness endpoint is an analysis of the freedom from recurrence of typical CTI dependent atrial flutter OFF Class I/III antiarrhythmic drugs (AADs) at 30-days post index procedure measured by a 24-hour continuous electrocardiogram (ECG) monitor.

6.4 Clinical Study Duration

The study is anticipated to take approximately 12-months to enroll and will include a 30-day follow-up period. Total study duration is anticipated to be 12-18-months. The per patient study duration is expected to be approximately 6-weeks.

6.4.1 Clinical Study Sample Size

The sample size consists of 110 mITT subjects, based on using a one-sided α of 0.05 and at least 90% power for the comparison of each primary endpoint against the corresponding performance goal. A maximum of 120 mITT subjects will be enrolled.

6.4.2 Clinical Study Site Enrollment

Enrollment at any single clinical center will be limited to 20% of the maximum enrollment. Clinical centers will be informed in writing by the Sponsor when they have met any of the enrollment limits.

6.5 Clinical Study Sites

TBD

6.6 Subject Population

The subject population will consist of men and women 18 years or older, presenting for a *de novo* cavotricuspid ablation for symptomatic typical atrial flutter.

6.6.1 Inclusion Criteria

A potential study subject will meet all of the following inclusion criteria:

- 1. Subjects are clinically indicated for de novo catheter ablation of typical atrial flutter.
- 2. At least one (1) documented episode of typical flutter within 180-days (6 months) prior to enrollment, documented by 12-lead ECG.
- 3. Age 18 years or older at time of consent.

4. Subjects are willing and able to provide written informed consent to participate in the study and agree to comply with all follow-up visits and evaluations.

6.6.2 Exclusion Criteria

A potential study subject who meets any of the following criteria will be excluded from participation:

- 1. In the opinion of the Investigator, any contraindication to the planned atrial ablation, including contraindications to anticoagulation therapy and any other significant uncontrolled or unstable medical condition (e.g. sepsis, acute metabolic illness, chronic kidney disease).
- 2. Inability to document cavotricuspid isthmus conduction.
- 3. Any prior right atrial cavotricuspid isthmus ablation.
- 4. Any cardiac ablation for non-atrial flutter arrhythmias within 90 days prior to enrollment.
- 5. Any patient scheduled or anticipating an AF ablation within the follow-up period.
- 6. Administration of oral amiodarone within 120 days prior to procedure excluding a one-time IV/oral administration of < 2000 mg in a 24-hour period.
- 7. Cardiac surgery within 60 days prior to enrollment.
- 8. ST-elevation myocardial infarction (STEMI) within 60-days prior to enrollment.
- 9. Current unstable angina.
- 10. Documented atrial or ventricular tumors, clots, thrombus, within 30-days prior to enrollment.
- 11. Any history of a known hematologic disorder (bleeding/clotting).
- 12. Implantation of permanent leads of an implantable device in or through the right atrium within 90-days prior to enrollment.
- 13. Subjects with New York Heart Association (NYHA) Class IV heart failure within 6months prior to enrollment.
- 14. Subjects with an ejection fraction less than 30% within 90-days of enrollment.
- 15. Percutaneous Transluminal Coronary Angioplasty (PTCA) within 30-days of enrollment.
- 16. Clinically significant moderate to severe structural heart disease (including tricuspid valve regurgitation, tricuspid valve stenosis, tricuspid valve replacement, Ebstein's anomaly, or other congenital heart disease) that would preclude catheter introduction and placement, as determined by the Investigator.
- 17. Any cerebral ischemic/infarct event (excluding transient ischemic attacks) within 180 days prior to enrollment.
- 18. Body Mass Index (BMI) >42 kg/m².

- 19. International Normalized Ratio (INR) > 3 (required for patients taking warfarin).
- 20. Severe uncontrolled systemic hypertension (systolic pressure > 240 mm Hg) within the last 30-days.
- 21. Women who are pregnant or plan to become pregnant within the course of their participation in the investigation.
- 22. Current enrollment in any other study protocol where testing or results from the study may interfere with the procedure or outcome measurements for this study.
- 23. Any other condition that, in the judgment of the Investigator, makes the patient a poor candidate for this procedure, the study or compliance with the protocol (includes vulnerable patient population, mental illness, addictive disease, terminal illness with a life expectancy of less than two years, extensive travel away from the research center).

6.7 Clinical Study Enrollment Definitions

For the purposes of this clinical study, the following definitions regarding the status of a subject will apply:

Enrolled Subject – Any subject who has signed an informed consent form, is deemed study eligible by meeting all of the inclusion and none of the exclusion criteria up to the point of the procedure.

[figure not shown]
Pre-procedure Testing Failure (PPT) – An enrolled subject who has presented for the procedure in any rhythm other than sinus rhythm or typical atrial flutter and has not undergone venous access. These subjects will be treated per the recommendations of the study physician and exited from the study. No use of the investigational device is allowed. A Study Exit electronic case report form (eCRF) will be completed.

Intent-to-Treat Failure Subject (ITT) – Any enrolled subject who has the venous access portion of the ablation procedure initiated and up to the point of completion of the right-atrial access but prior to any RF application with the investigational device. The ITT population will be followed for safety reasons through the 7-day follow-up visit. ITT subjects that the AcQBlate FORCE Catheter has been inserted into will be included in the safety data analysis but excluded from the efficacy data analysis. All other ITT patients will be excluded from any safety or efficacy data analysis. In addition to the Discharge eCRF and the 7-day Follow-up eCRF, a Study Exit eCRF will also be completed. The ITT population may include:

• At the time of the procedure, if the subject does not demonstrate conduction through cavotricuspid isthmus, the subject will be exited from the study and followed for safety through the 7-day follow-up visit.

• At the time of procedure, if atrial fibrillation is initiated during the process of inducing typical AFL, a direct current cardioversion (DCCV) may be performed to attempt conversion to sinus rhythm so that the CTI conduction portion of the study may proceed. If during confirmation of CTI conduction, the investigator determines that further ablation beyond the CTI is warranted the subject will be exited from the study and followed for safety through the 7-day follow-up visit.

Modified Intent-to-Treat Subject (mITT) – Any enrolled subject who initiates the ablation procedure using the AcQBlate Force Sensing System. An initiated ablation procedure is defined as a procedure where the AcQBlate Force Sensing System is used for the ablation procedure irrespective if a non-investigational device was used to complete the ablations. mITT subjects will be followed for all study outcome measures for the full duration of the clinical study and will comprise the data set for the Primary Safety and Efficacy Endpoints.

Clinical Study Enrollment Definitions Flow Chart

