5.6 Analysis of Study Endpoints

5.6.1 Primary Safety Endpoint

The primary safety endpoint is defined as the proportion of mITT and select ITT Failure subjects (i.e., subjects who had the AcQBlate FORCE Catheter inserted) who are free from a composite list of pre-specified device/procedure related SAEs that occur through 7-days post ablation procedure. Subjects who do not have evidence of a SAE/SADE from the composite list of safety events will be considered a success.

Serious adverse events that meet the definition for Primary Safety Endpoint are pre-defined and include:

- Death
- Cardiac tamponade/perforation
- Myocardial infarction
- Stroke
- Systemic embolism
- Major access site complications
- Major bleeding requiring transfusion
- Complete heart block
- Other SAEs/SADEs adjudicated by an independent review as "probably or definitely related" to the Investigational device.

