5.6.3 Other Safety Analyses

Adverse events (AE) will be reported for all mITT and ITT Failure subjects.

Sta	atistical Analysis Plan	Page	12 of 14
Sponsor	Study		Version
ACUTUS Medical	AcQBlate Force Sensing Ablation System US IDE/EU Study for Atrial Flutter (AcQForce Flutter & AcQForce Flutter-EU)		2.0

Individual device/procedure related SAEs at 7-days will be analyzed by event frequencies and proportions of subjects. Total and individual non-serious, device/procedure related AEs at 30-days will also be analyzed by event frequencies and proportion of subjects. Adverse events will be analyzed in terms of their severity, action taken, and duration to resolution.

Device Deficiency Reports will be analyzed for frequencies of safety events and proportion of subjects as part of the safety analyses.

All AEs and SAEs will be tabulated with the number of events and subjects with event for each event type and overall. The rate of all AEs and SAEs reported in the study will be reported as well as the rates at 7 and 30 days. AEs and SAEs will also be summarized by relatedness and severity. Adverse events leading to death or study discontinuation will be provided in listing format. Rates will be reported as the number of subjects who experience at least one event during the analysis interval out of the total number of subjects with follow-up to the beginning of the analysis interval.

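### The primary safety set is fixed only when the investigational catheter is inserted, so a procedure-related event that stops the case before insertion is left out of the endpoint

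*Combined protocol and SAP*

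**What the plan says.** **Who is an ITT Failure subject.** Protocol 6.7 starts this status at venous access: "Any enrolled subject who has the venous access portion of the ablation procedure initiated". It ends before any RF application. The two situations listed there (no CTI conduction; ablation beyond the CTI judged necessary) are given as examples, so a case stopped by a complication also meets the definition.

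**Who counts for safety.** Protocol 6.7 says "ITT subjects that the AcQBlate FORCE Catheter has been inserted into will be included in the safety data analysis", and for the rest "All other ITT patients will be excluded from any safety or efficacy data analysis". SAP 5.6.1 defines the primary safety set as mITT plus "select ITT Failure subjects (i.e., subjects who had the AcQBlate FORCE Catheter inserted"). Protocol 8.2 and 8.2.1 use the same mITT-plus-select-ITT set.

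**What counts as an event.** Protocol 6.3.1 counts subjects "free from a composite list of pre-specified device/procedure related Serious Adverse Events (SAEs) that occur through 7-days post ablation procedure". The composite names "Major access site complications", along with major bleeding and tamponade/perforation. No section requires the event to come after insertion, and protocol 7.8 times the procedure from first venous access.

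**Where the documents disagree.**
- The mITT definition in protocol 6.7 names mITT alone as the data set for both primary endpoints. SAP 5.2 assigns mITT to efficacy only.
- SAP 5.2 excludes ITT Failure subjects from efficacy only, and SAP 5.6.3 says "Adverse events (AE) will be reported for all mITT and ITT Failure subjects". Both conflict with the protocol's exclusion from every safety analysis.
- Protocol 8.5 refers to select ITT subjects. SAP 5.6.1.2 and 5.8 refer to ITT Failure subjects without that restriction.

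**The concern.** The endpoint covers a period that begins at venous access, but membership of its analysis set is settled later, at catheter insertion. Between the two, what happens to the subject can decide whether the subject is analysed. Take an access-site complication that needs surgery. If the operator continues and inserts the study catheter, the subject is a primary safety failure. If the complication ends the case, the subject leaves both numerator and denominator.

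A dropped event can only make the observed rate look better, so the bias runs towards passing. What is at stake is one of the two hypotheses that define study success (protocol 8.4), in a study meant to support a PMA, with a pass mark of only a few events. The tipping-point analysis in SAP 5.6.1.2 does not cover this, because it deals with missing data and these outcomes are observed.

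**Working it through.** **Inputs.** Performance goal 93.0%; rejection if the one-sided 95% Clopper-Pearson lower bound exceeds it (protocol 8.2.1, SAP 5.6.1.1). Expected rate 98.5% (protocol 8.1). Sample size 110, maximum 120 mITT (protocol 8.8).

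**1. Reproduce the planned size.** One-sample z test with the null variance at the critical value:

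n = [(1.645·√(0.93·0.07) + 1.282·√(0.985·0.015)) / 0.055]² = 109.47, rounded up to 110.

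This matches the plan. It needs 98.5% as the expected rate; the 97% in the text of protocol 8.8 gives 255 by the same formula, which is a separate matter.

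**2. Find the pass mark.** With f failures in n subjects, the lower bound is the 5th percentile of a Beta(n−f, f+1) distribution.

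| Failures / n | Lower bound | Result |
|---|---|---|
| 3/110 | 93.10% | pass |
| 4/110 | 91.87% | fail |
| 3/120 | 93.67% | pass |
| 4/120 | 92.53% | fail |

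Three failures is the limit at both sizes.

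**3. Restore one dropped event to a just-passing result.** The subject returns to numerator and denominator.

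| Failures / n | Lower bound | Result |
|---|---|---|
| 4/111 | 91.94% | fail |
| 4/121 | 92.60% | fail |

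Four failures first pass at n=129 (93.05%). Reversing the failure would take 129 − 111 = 18 further event-free subjects, or 129 − 121 = 8.

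**4. Effect on the false-pass rate.** Let the true event rate among all subjects with venous access be 7%, exactly on the null. Let s be the share of events that occur before insertion and stop the case. The documents do not give s, so it is an assumption. Dropped subjects leave numerator and denominator, so the event rate among those analysed is

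q = 0.07(1 − s) / (1 − 0.07s).

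The false-pass rate is P(X ≤ 3) for X ~ Binomial(n, q).

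| s (assumed) | q | n=110 | n=120 |
|---|---|---|---|
| 0 | 0.0700 | 4.6% | 2.8% |
| 5% | 0.0667 | 5.9% | 3.7% |
| 10% | 0.0634 | 7.6% | 5.0% |
| 20% | 0.0568 | 12.3% | 8.6% |

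**5. Power if one more subject is counted.** At a true 98.5%, exact power is 91.6% at n=110 and 91.3% at 111; it is 89.3% at 120 and 89.0% at 121. A wider set costs almost nothing if the device performs as planned.

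**The case against.** **A device-exposed set is a legitimate choice.** The objective concerns the system when used to ablate, and restricting safety to subjects in whom the catheter was inserted fits that. This would stand for a device-related endpoint. Here the endpoint is device- or procedure-related and names access-site complications, and the documents give no reason for the mismatch.

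**The events are not hidden.** A reader might infer from protocol 6.7 that such an event disappears from all reporting. The documents do not support that: SAP 5.6.3 tabulates adverse events for every ITT Failure subject. What stands is the absence from the primary endpoint and success criterion, plus a conflict between protocol and SAP.

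**The effect may be small.** The study catheter may itself be used for mapping before ablation (protocol 5.6), so the window before insertion may be short. A reversal needs a result on the margin and a dropped event together: at a true 98.5% and a 5-10% loss, this happens in about 1-2% of trials at n=110. That stands, and it limits the weight of step 3.

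**Table 2 does not supply the share.** A reader might take its 8 access-site or perforation/tamponade events out of 28 (29%) as the fraction at risk. That counts event types, not events before insertion that ended a case. Five of the eight come from one contact-force study that also treated paroxysmal atrial fibrillation; without it the figure is 3 of 23 (13%).

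**Adding only the never-inserted subjects who had events** would also make inclusion depend on outcome, with bias in the other direction. That objection is right, and the fix avoids it.

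**Conclusion.** The concern holds for the primary safety endpoint and the success criterion. A composite event after venous access that stops the case before insertion is not counted, and the omission can only favour passing. With a limit of three failures at n=110 and n=120, one such event can decide a marginal result.

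The expected size is uncertain. Under an assumed 5-10% loss, the false-pass rate exceeds the nominal 5% at n=110 (5.9-7.6%) but not at n=120 (3.7-5.0%). A reader might infer that the error rate is certainly inflated above 5%; that depends on the final n and on a share the documents do not give. The calculation also assumes that every subject without such an event goes on to insertion. This is a cheap improvement to the plan, not evidence that its safety conclusion would be wrong.

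**What to change.** 1. **Protocol 6.7.** Exclude never-inserted ITT Failure subjects from the efficacy analysis only, and state that their adverse events are reported as in SAP 5.6.3. Use one definition of the safety set in the mITT definition of 6.7, in protocol 8.2, 8.2.1 and 8.5, and in SAP 5.6.1, 5.6.1.1, 5.6.1.2 and 5.8.
2. **SAP 5.6.1.2.** Prespecify an analysis of the same composite endpoint in all subjects with venous access initiated: mITT plus all ITT Failure subjects, with and without events. Report its one-sided 95% Clopper-Pearson lower bound beside the primary bound.

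Do not add only the never-inserted subjects who had events.

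**Cost.** A few sentences in each document and one extra table row. ITT Failure subjects are already followed through the 7-day visit, with Discharge and 7-day eCRFs, so no new data are needed. The downside for the sponsor is that the reported safety rate may be slightly less favourable.
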